9.2 Secondary Efficacy Analysis

All secondary efficacy analyses will be provided twice, based on the response assessment of the Investigator and based on the central review assessment.

The analysis of ORR as described in section 9.1 will be additionally be stratified by Fc γ RIIIa and Fc γ RIIa polymorphism.

Fc γ R subgroups will comprise the heterozygous population and each different homozygous population, as well as the combined heterozygous plus low affinity homozygous Fc γ R populations. Subgroups with fewer than five patients will not be analysed.

These stratifications will be done for the overall analysis population as well as by NHL subtype.

The overall stable disease rate will be analyzed analogously to the overall response rate as described in Sect. 9.1.

Time to progression and progression-free survival will be analyzed using Kaplan-Meier methods. Kaplan-Meier tables for progression-free survival and time to progression will contain number of patients, number of patients with an event (non-censored patients), percentage of patients with an event, median time [months], 25% and 75% quantile and 95%-

confidence intervals for median (Brookmeyer and Crowley, 1982).

Moreover, the percentage of patients having an event until 2, 4, 6, and 12 months together with the corresponding 95%-confidence intervals will be retrieved.

In the main analysis of PFS, only patients with radiologically confirmed progression or death within 2 months of the last radiological assessment will be counted as having had a PFS event. A sensitivity analysis will also be done in which patients who were withdrawn from the study because of disease progression will be included as having a PFS event, even in the absence of radiological confirmation of disease progression.

Duration of response and time to response (Investigator) and duration of best overall response and time to response (Central Read) will also be analyzed using Kaplan-Meier estimates for median, 25% and 75% quantile. The analysis of duration of response will be restricted to the subgroup of responders. Moreover, the percentage of patients having an event after 2, 4, 6, and 12 months together with the corresponding 95%-confidence intervals will be retrieved from the Kaplan Meier curve.

The analysis of duration of response and time to response will be presented for all responders overall.

Kaplan-Meier plots for time to progression, progression-free survival, time to response, and duration of response will be provided.

Data on tumour lesion size will be presented with descriptive statistics and individual data listings. This will include the area of indicator lesions at baseline, the area of indicator lesions at nadir, and the difference between those two areas. The data on lesion size will be presented separately for the two central reviewers. The area of indicator lesions will be examined as follows:

1. Analysis across all points in time:

- Absolute values and both absolute and relative changes (from baseline) will be summarized for each visit:
 - Separated by NHL subtype
 - For the group of FL patients + other indolent lymphoma patients
- A graph showing the individual relative changes over time will be generated separately for all NHL subtypes and for both central readers. The best overall response of each individual will be indicated by colour coding.

2. Analysis comparing baseline and nadir:

CONFIDENTIAL

03 April 2019

- The area of indicator lesions will be reported at baseline and at nadir. The absolute value and both the absolute and relative difference between baseline and nadir will be reported (separated by NHL subtype, i.e., DLBCL, FL, MCL, other indolent NHL, and for the group comprising FL patients + other indolent lymphoma patients).
- A “waterfall plot” indicating the best change (%) for indicator lesions will be generated separately for both central readers. Shading of the bars will indicate the NHL subtype. The plot will be produced in the following two versions:
 - Comprising all NHL subtypes (i.e., DLBCL, MCL, FL, and other indolent NHL)
 - Comprising only DLBCL, FL, and other indolent NHL

A listing of total time on study (time from first dose of MOR208 to date of last tumour assessment), composed of time to response and duration of response, will be provided. In addition, time on study will be tabulated as a continuous variable. No censoring will be applied to total time on study.

All analyses will be provided by NHL subtype, the combined groups of FL and other indolent NHL, and overall, if not specified otherwise.

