14.5.1 Secondary Efficacy Variables and Analyses

The proportion of patients in each subtype with stable disease (SD) will be summarized after the second cycle.

The DoR will be the time from first meeting of criteria for response (ie CR or PR) to first documentation of relapse or progression.

The TTP is defined as the time from study entry (first dosing) until documented lymphoma progression or death as a result of lymphoma. Patients not experiencing a progression will be censored at the last NHL assessment. Deaths from other causes are censored at the time of death. The data will be summarized using Kaplan-Meier estimates.

Progression-free survival is defined as the time from study entry (first dosing) until lymphoma progression or death as a result of any cause. Patients not experiencing a progression or death will be censored at the last NHL assessment. The data will be summarized using Kaplan-Meier estimates.

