17.4 Response Criteria

The response criteria in this study are those defined in the table below. All of them are based on the International Working Group Response Criteria (2007).

Table 8 Response Criteria

Response	Definition	Nodal masses	Spleen, liver	Bone marrow
CR	Disappearance of all evidence of disease	a) FDG-avid or PET positive prior to therapy; mass of any size permitted if PET negative b) Variable FDG-avid or PET negative; regression to normal size on CT	Not palpable, nodules disappeared	Infiltrate cleared on repeat biopsy; if indeterminate by morphology, immunohistochemistry should be negative
PR	Regression of measurable disease and no new sites	≥ 50% decrease in SPD of up to 6 largest dominant masses; no increase in size on CT a) FDG-avid or PET positive prior to therapy; one or more PET positive at previously involved site b) Variable FDG-avid or PET negative; regression on CT	≥ 50% decrease in SPD of nodules (for single nodule in greatest transverse diameter); no increase in size of liver or spleen	Irrelevant if positive prior to therapy; cell type should be specified
SD	Failure to attain CR/PR or PD	a) FDG-avid or PET positive prior to therapy; PET positive at prior sites of disease and no new sites on CT or PET b) Variable FDG-avid or PET negative; no change in size of previous lesions on CT		
Relapsed disease or PD	Any new lesion or increase by ≥ 50% of previously involved sites from nadir	Appearance of a new lesion(s) > 1.5 cm in any axis, ≥ 50% increase in SPD of more than one node, or ≥ 50% increase in longest diameter of a previously identified node > 1cm in short axis Lesions PET positive if FDG-avid lymphoma or PET positive prior to therapy	> 50% increase from nadir in the SPD of any previous lesions	New or recurrent involvement

Abbreviations: CR, complete remission; FDG, [¹⁸F]fluorodeoxyglucose; PET, positron emission tomography; CT, computed tomography; PR, partial remission; SPD, sum of the product of the diameters; SD, stable disease; PD, progressive disease

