Duration of response (Investigator): Duration of response will be defined as the time from date of first response (CR or PR) until first date that recurrence or progressive disease is objectively documented. The duration of response will be calculated in the subgroup of all patients showing any response; confirmation of response will not be required. Patients who showed a response but did not show PD or recurrence until end of study or before study discontinuation (i.e. patients who are at least stable at their last tumor assessment) are considered censored at the timepoint of last response assessment. Deaths due to causes other than progression of disease are to be reported as SAEs and are censored for duration of

Statistical Analysis Plan Final Version 4.0

response analysis at the date of last tumor assessment before death. The cause of death has to be recorded as free text by the Investigator on the eCRF study completion page. If the cause of death does not explicitly state whether death is related to progression of disease, a query will be raised to ask the investigator to classify the relationship to disease (yes/no). Morphosys Drug Safety will assess the causality of the SAE by reviewing the corresponding SAE documents.

Time to response (Investigator): Time to response will be defined as the time from Cycle 1, Day 1 (first administration of study drug) until the date of first response (CR or PR). Patients who do not have a response to treatment will be censored at the date of their last tumor assessment.

Time to progression (Investigator): Time to progression is defined as the time from Cycle 1, Day 1 (first administration of study drug) until date of first tumor progression (which is entered in the tumor assessment module). Patients who do not show any documented progression (which is entered in the response assessment module of the eCRF) before the end of study or before study discontinuation or before death are considered censored using the last date with a tumor assessment as censoring date (irrespective of when the patient died). Deaths due to causes other than disease progression are censored.

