Progression-free survival (Investigator): Progression-free survival is defined as the time from Cycle 1, Day 1 (first administration of study drug) until date of first tumor progression (which is entered in the response assessment module of the eCRF) or date of death from any cause. If the patient does not show any documented progression (which is entered in the tumor assessment module) before death, the date of progression will be the date of death if death occurs within 2 months after the last date with a tumor assessment. If death occurs after 2 months after the last date with a tumor assessment or the patient did not progress or die until end of study or before withdrawal, the patient will be analyzed as censored using the last date with a tumor assessment as censoring date.

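### SAP 9.2 restricts main PFS to radiologically confirmed progression, narrower than the protocol and SAP 7.3.4.1 and undeclared, so an investigator-recorded PD can be a TTP event yet censored in PFS

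*SAP*

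**What the plan says.** - **Protocol 14.5.1** (10.6 to the same effect): "Progression-free survival is defined as the time from study entry (first dosing) until lymphoma progression or death as a result of any cause". No form of evidence for progression is required.
- **Protocol 17.4, Table 8:** the row for relapsed or progressive disease has a bone marrow column that reads "New or recurrent involvement". Progression can therefore be met without a change on a scan.
- **SAP 7.3.4.1, investigator PFS:** time "until date of first tumor progression (which is entered in the response assessment module of the eCRF) or date of death from any cause". There is no radiology condition. Deaths have a separate limit: "If death occurs after 2 months after the last date with a tumor assessment", the patient is censored at that assessment.
- **SAP 7.3.4.1, investigator TTP:** time "until date of first tumor progression (which is entered in the tumor assessment module" of the eCRF. Again there is no radiology condition.
- **SAP 9.2, main PFS analysis:** "only patients with radiologically confirmed progression or death within 2 months of the last radiological assessment will be counted", that is, treated as PFS events. The section then plans a sensitivity analysis, in which patients withdrawn for disease progression "will be included as having a PFS event, even in the absence of radiological confirmation of disease progression".
- **SAP Section 12** lists three changes from the protocol: the PK population, central-read ORR, and the dropped CD19 stratification. The PFS restriction is not among them.

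**The concern.** PFS and TTP share a starting point and a progression component, and PFS adds deaths. Every TTP event should therefore also be a PFS event, and the PFS curve should not lie above the TTP curve. Under SAP 9.2 that can fail in the investigator version, because a recorded PD without radiological confirmation counts for TTP and is censored for PFS.

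Censoring a patient because progression was found by a route other than imaging is informative, and it pushes the Kaplan-Meier curve up. The outputs exposed are the PFS median and quartiles and the 2-, 4-, 6- and 12-month estimates in SAP 9.2. The PFS subgroup hazard ratios in SAP 9.3 are also exposed if they use the main rule. MCL is the most exposed cohort, since protocol 8.1 admits MCL patients with only evaluable sites such as marrow or peripheral blood.

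**Working it through.** **1. The rules side by side, for progression only (investigator version)**

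| Patient | TTP, SAP 7.3.4.1 | PFS, protocol 14.5.1 and SAP 7.3.4.1 | Main PFS, SAP 9.2 |
|---|---|---|---|
| PD entered, shown on imaging | event | event | event |
| PD entered on marrow alone, scan not PD | event | event | censored |
| Withdrawn for progression, no PD entered | censored | SAP 7.3.4.1: censored; protocol: event if lymphoma progressed | censored (event in the sensitivity analysis) |

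The second row is the conflict. In the third row the two SAP endpoints agree, since both require an entry in the eCRF.

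**2. Is there a figure in the plan to reproduce?** No. The documents give no PFS median, event count or power, and no share of progressions expected to lack imaging. What follows is an illustration.

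**3. Inputs**

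- *Scan days, from the protocol schedule.* Cycle 2 Day 28 is day 56. Cycle 3 starts two weeks after Cycle 2 Day 22 (day 50), so on day 64, and its Day 28 is day 91. Follow-up 1 is four weeks later (day 119) and Follow-up 2 six weeks after that (day 161). Follow-up 3 has no response assessment (day 203). Follow-up 4 is three months later (day 294).
- *Assumed:* exponential progression times with a median of 180 days, no deaths, and a share f of progressions never confirmed on imaging, the same in all cohorts.
- *Dating:* a confirmed PD is dated at the next scan. An unconfirmed one is censored at the previous scan.

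**4. Formula.** The chance of progressing in interval i, given no earlier progression, is pᵢ = 1 − 2^(−Δᵢ/180):

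- days 0–56: 0.194
- days 56–91: 0.126
- days 91–161: 0.236
- days 161–294: 0.401

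Removing the unconfirmed share from the risk set gives an interval survival of (1 − pᵢ)/(1 − f·pᵢ). The last scan before 6 months is day 161 and the last before 12 months is day 294, so

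S_f = S₀ / ∏(1 − f·pᵢ), with S₀(161) = 2^(−161/180) = 0.538 and S₀(294) = 2^(−294/180) = 0.322.

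**5. Results**

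| f | ∏ to day 161 | 6-month PFS | ∏ to day 294 | 12-month PFS |
|---|---|---|---|---|
| 0 | 1 | 0.538 | 1 | 0.322 |
| 0.1 | 0.945 | 0.569 | 0.907 | 0.355 |
| 0.2 | 0.893 | 0.603 | 0.821 | 0.393 |
| 0.3 | 0.842 | 0.639 | 0.741 | 0.435 |

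A simulation of 20,000 patients on the same scan days gave 0.538, 0.571, 0.601 and 0.639 at 6 months, and 0.323, 0.357, 0.392 and 0.430 at 12 months, in agreement.

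**6. Sensitivity to dating.** If events are dated when they occur rather than at the next scan, and unconfirmed ones are still censored at the last assessment, a simulated true median of 6 months becomes 6.6, 7.2 and 8.1 months for f = 10%, 20% and 30%. If they are censored at the event date instead, the median is 6/(1 − f): 6.7, 7.5 and 8.6 months. The direction is the same throughout. At f = 0 nothing changes.

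**The case against.** **Radiologically confirmed may be loose wording.** SAP 7.3.4.1 measures the two-month death window from the last tumour assessment and SAP 9.2 from the last radiological assessment, so the SAP may use the terms interchangeably. It also names no variable that marks an investigator PD as radiologically confirmed. On that reading SAP 9.2 only means PD entered in the module, as opposed to a withdrawal reason. This is strained, because the sensitivity analysis is described by the absence of radiological confirmation, which treats imaging as the dividing line. The missing variable does stand, and it is a further reason to clarify.

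**The effect may be small.** Scheduled marrow examinations fall at visits that also require CT, although that scan need not show PD. Marrow is repeated only if the last marrow result was not CR, and measurable disease is mandatory outside MCL. SAP 7.3.4.1 also keeps a PD imaged after new therapy has started, so some clinical progressions are delayed rather than lost. All of this stands, and it means the affected share cannot be presumed large.

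**A reader might infer that progression often goes unconfirmed because the End of Study visit has no CT.** The documents do not support that. Protocol 10.5 places the visit four weeks after the visit at which progression was diagnosed, or four weeks after the last Cycle 2 dose when the Cycle 2 response, assessed with CT, was below SD. For patients who leave before any response assessment, protocol 10.6 asks for an evaluation about one month later, if possible.

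**The plan exposes the issue itself, and PFS is secondary.** The study is single-arm with no inferential testing, and asking for imaging in an open-label trial is defensible. The sensitivity analysis will show much of any difference. It does not make the main analysis coherent with TTP. It reaches only patients whose withdrawal reason is progression, while protocol 9.11.1 lists new cancer therapy and death as separate reasons. It also states no event date for the patients it adds.

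**Conclusion.** The inconsistency is in the text and needs no assumption. SAP 9.2 is narrower on progression than the protocol and than SAP 7.3.4.1, Section 12 does not declare it, and investigator TTP and main investigator PFS follow different progression rules. It should be corrected.

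The bias is only possible, and its size is unknown. The illustrative rise in 6-month PFS from about 54% to 57–64% rests on an assumed 10% to 30% unconfirmed share and an assumed 6-month median. Neither is in the documents.

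Three stronger readings are not supported:

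- **That PFS is overstated.** It could be. This requires PDs that are recorded but not seen on imaging at the same date.
- **That every patient withdrawn for clinical progression counts for TTP but not PFS.** Without a PD entry, the patient counts for neither main endpoint.
- **That all PFS results are affected.** The central read uses scans for both endpoints, so this split does not arise there.

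The conflict within the SAP concerns progression. On deaths, SAP 9.2 broadly agrees with SAP 7.3.4.1, since both apply a two-month window.

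**What to change.** In SAP 9.2:

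1. Base the main investigator PFS analysis on the SAP 7.3.4.1 progression rule: any PD the investigator records under protocol Table 8, on the recorded date. This is the rule TTP already uses.
2. Report PFS limited to radiologically confirmed progression as a sensitivity analysis, and say how confirmation of an investigator PD is identified. Keep the radiological rule for the central read.
3. Keep the planned sensitivity analysis that adds patients withdrawn for progression without a recorded PD, and state the event date used for them. Counting them as events in the main analysis would go beyond SAP 7.3.4.1 and is debatable, so it is not proposed.

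If the sponsor prefers to keep the radiological rule as main, the minimum is to declare it in Section 12 and apply the same progression rule to investigator TTP.

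The cost is SAP wording and some programming, with no new assessments. The downside is that investigator PFS may be slightly shorter.

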10.2 Main Treatment Phase (Cycles 1-3)

Only patients fulfilling all inclusion and none of the exclusion criteria should be enrolled.

The schedule of required procedures for each treatment day is detailed in [Table 2](#). Clinical site study days are Days 1, 2, 8, 15, and 22 for Cycle 1 and Days 1, 8, 15, 22, and 28 for Cycle 2. Patients qualifying for Cycle 3 will have visits on Days 1, 8, 15, 22, and 28 of this cycle.

During the first two 28-day cycles, patients will receive a total of 8 infusions: each 28-day cycle will consist of a MOR00208 infusion on Day 1, Day 8, Day 15 and Day 22 of the cycle.

- Patients with a response of at least SD on Cycle 2, Day 28, will qualify for 1 further cycle of MOR00208 (infusions on Day 1, Day 8, Day 15 and Day 22 of the 28-day cycle). This potential Cycle 3 should start 2 weeks \pm 1 day after Cycle 2, Day 22.

Before dosing, premedication as detailed in [Section 9.5](#) should be administered.

Clinical assessments, physical examinations and laboratory evaluations (instead of emergency lab) may be performed within 24 hours before administration of MOR00208 (except PK and anti-MOR00208 antibodies); assessments for Cycle 3 should only be performed if patient qualifies for the respective study drug administration:

- Assessment of AEs and concomitant medication at all visit days (see [Section 9.8](#))
- Assessment of body weight at all visit days
- Physical examination including palpable tumor assessment, general appearance, skin, head, eyes, ears, nose, throat, lungs, breasts and axillae (if applicable including bi-dimensional measurement of cervical, supraclavicular, axillary and inguinal lymph nodes), cardiovascular system, back and spine, abdomen (if applicable including spleen size below the costal margin), extremities, infusion site, lymph nodes and neurological examination at Day 1 (predose) and Day 22 of Cycle 1; and Day 28 of Cycles 2 and 3.
- ECOG performance status (Day 1 and 15 of Cycles 1 to 3)

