 - Cycle 1, Day 1 : before infusion, at the end of infusion (\pm 10 minutes) and 1 hour (\pm 10 minutes), 4 hours (\pm 10 minutes) and 24 hours (\pm 1 hour) after end of first MOR00208 infusion
 - Cycle 1, Days 8, 15 and 22; Cycles 2 and 3, Days 8 and 22: before infusion and 1 hour after the end of infusion (\pm 10 minutes)
 - Cycles 2 and 3, Day 28
 - B-, T- and NK cell flow cytometry before infusion on Days 1, 8, 15 and 22 of Cycle 1 and on Days 1, 15 and 28 of Cycles 2 and 3.
 - Anti-MOR00208 antibodies before infusion on Day 1 of Cycles 1 to 3.
 - Serum immunoglobulin levels before infusion on Day 1 of Cycle 1 and Day 22 of Cycles 1 to 3.

- If anti-HBc is positive: HBV-DNA as per assessment schedule. (Please see also Section 9.5.2.)
- Laboratory assessments from urine sampling before infusion (Day 1 preinfusion assessments will be considered baseline assessments):
 - Urinalysis on Day 1 of Cycles 1 to 3.
 - Urine pregnancy test in women of childbearing potential on Day 1 of Cycles 1 to 3.
- FcγRIIIa and FcγRIIa polymorphism (mucosal cheek swab) before infusion on Day 1, Cycle 1 (optional, see Section 10.9.7)
- 12-lead ECG on Day 1 of Cycle 1, and on Days 8 and 22 of Cycles 2 and 3

10.3 Follow-up Phase until Follow-up Visit 12

All patients who performed treatment Cycle 3 should have a follow-up visit 4 weeks after end of the last treatment cycle (4 weeks \pm 2 days after Cycle 3 Day 28). Patients should return for further follow-up visits until relapse of the lymphoma or for a maximum of 4 years. The second and third follow-up visit should be scheduled 6 weeks \pm 1 week following the previous visit, the fourth to sixth follow-up visit should be scheduled 3 months \pm 2 weeks following the previous visit, further follow-up visits should then be scheduled every 6 months. If not otherwise indicated, the following assessments should be performed at every follow-up visit:

- Patients with an ongoing response of at least PR after Cycle 3 may receive maintenance treatment with MOR00208 (12 mg/kg either every second week or monthly). Before administration, blood parameters (hematology, serum chemistry) should be evaluated in the local lab according to local guidelines/practice for the administration of monoclonal antibodies. A urine pregnancy test should be performed for women of childbearing potential. These lab results will only be captured in the eCRF if the administration visits coincide with the planned follow-up visits.

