Patients who have not progressed after four years of treatment with MOR00208 (ie, after Follow-up Visit 12 as described above) may continue receiving the IMP thereafter, until progression, based on the decision of the treating physician. The treatment frequency (during the follow-up period as described above) should be maintained.

Prior to each administration of MOR00208, the following assessments should be performed at a local laboratory:

- Assessment of body weight
- Haematology including CBC with differential and platelet count and serum chemistry

- β -HCG urine pregnancy test for women of childbearing potential (only urine pregnancy test is to be done if regular follow-up visit coincides with maintenance treatment visit; otherwise, serum pregnancy test should be done)
- Vital signs (pulse, systolic and diastolic blood pressure, body temperature, and respiratory rate) hourly
- Physical examination
- If anti-HBc was positive earlier: HBV-DNA should be measured every six months. (Please see also Section 9.5.2.)

Only the data on AEs, SAEs, and concomitant medications will be collected in the study database during this period.

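### In analyses run after patients pass Follow-up Visit 12, the sensitivity PFS makes follow-up depend on outcome and can distort the tail of its Kaplan-Meier curve

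*SAP*

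**What the plan says.** Four rules meet here.

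- **Treatment and data after FU12 (Protocol 10.4).** The section covers "Patients who have not progressed after four years of treatment with MOR00208 (ie, after Follow-up Visit 12 as described above"), who may continue MOR00208 until progression. On data it says: "Only the data on AEs, SAEs, and concomitant medications will be collected in the study database during this period". Table 2 shows no CT/PET or response assessment at maintenance visits beyond FU12.
- **Censoring (SAP 7.3.4.1; the same rule for the central read in 7.3.4.2).** Without progression or a qualifying death, "the patient will be analyzed as censored using the last date with a tumor assessment as censoring date".
- **Main and sensitivity PFS (SAP 9.2).** The main analysis needs radiological progression, or death within 2 months of the last radiological assessment. In the sensitivity analysis "patients who were withdrawn from the study because of disease progression will be included as having a PFS event", with no scan required. The SAP gives no date for that event, no upper time limit, and no matching change to censoring for patients who remain in remission.
- **Withdrawal reason (Protocol 9.11.1, SAP 8.1).** The primary reason goes on the eCRF, with disease progression as a listed option. The SAP tabulates the reasons for discontinuing during maintenance.

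SAP 4.1 plans the main analysis on a July 2015 data cut, allows later analyses, and schedules a further set after the last end-of-study (EOS) visit.

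**The concern.** Kaplan-Meier estimation needs a patient's length of observation to be unrelated to prognosis. Past FU12 the sensitivity PFS can break this. A patient in remission on treatment leaves the risk set at FU12, however long the remission then lasts. A patient who is later withdrawn for progression stays in the risk set until that event. Observation beyond FU12 is then granted only to those who fail.

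The patients concerned are the long-term responders, who carry the evidence for durable benefit. In cohorts planned at 10 to 30 patients, a handful of them determine the whole tail. A sensitivity analysis meant to support the main PFS could show a late drop produced by the rules and not by the disease.

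**Working it through.** **1. When FU12 falls.** Take Cycle 1 Day 1 as day 0 and 30.4375 days per month (SAP 7.1).

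- Cycle 2 Day 22 is day 49. Protocol 10.2: "This potential Cycle 3 should start 2 weeks" after it, so Cycle 3 Day 1 is day 63 and Cycle 3 Day 28 is day 90.
- Protocol 10.3: "All patients who performed treatment Cycle 3 should have a follow-up visit 4 weeks after end of the last treatment cycle", so FU1 = 90 + 28 = day 118.
- "The second and third follow-up visit should be scheduled 6 weeks" after the previous visit: FU3 = 118 + 2 × 42 = day 202.
- "the fourth to sixth follow-up visit should be scheduled 3 months" after the previous visit: FU6 = 202 + 3 × 91.3 = about day 476.
- Later visits are 6-monthly: FU12 = 476 + 6 × 182.6 = about day 1,572.

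Measured from Cycle 3 Day 28 this is 1,482 / 365.25 = 4.06 years, and from FU1 1,454 / 365.25 = 3.98 years, which reproduces the protocol's four years. On the PFS clock, which starts at first dose, it is 1,572 / 365.25 = 4.30 years (51.6 months). Using every stated visit window cumulatively gives 4.13 to 4.48 years. Response is assessed at FU2, FU4, FU5 and every later follow-up visit, so FU12 is the last scheduled assessment with imaging.

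**2. The general result.** Let S be the estimate at FU12, *m* the number then progression-free, and *k* the number of these later withdrawn for progression. Each event multiplies the curve by (1 − 1/number at risk).

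- *Sensitivity rule, event dated at withdrawal:* only the *k* future progressors are at risk after FU12. The factors are (1 − 1/k) × (1 − 1/(k−1)) × … × (1 − 1/1) = 0, for any *k* of 1 or more and any *m*.
- *Everyone followed past the last event:* S × (m − k)/m.
- *Event back-dated to FU12:* S × (m − k)/m, so zero only if all *m* progress.
- *Main PFS, or a common cut at FU12:* stays at S.

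**3. Illustrations on assumed data** (the documents give no PFS event counts).

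*A.* 30 patients: 22 events by 40 months, 2 censored early, 6 progression-free at FU12, one withdrawn for progression at 72 months. With both early censorings placed just after the third event, S = 27/30 × 6/25 = 0.216. As above, the sensitivity rule gives 0.216 × (1 − 1/1) = 0. With the other five followed to 84 months it is 0.216 × 5/6 = 0.180.

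*B.* 30 patients: 20 events by 2 years, 10 progression-free at FU12, S = 10/30 = 0.333, withdrawals from year 5 on.

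| Later withdrawals (k of 10) | Sensitivity rule, dated at withdrawal | Equal follow-up, or back-dated to FU12 | Common cut at FU12 |
|---|---|---|---|
| 1 | 0 | 0.300 | 0.333 |
| 2 | 0 | 0.267 | 0.333 |
| 3 | 0 | 0.233 | 0.333 |
| 5 | 0 | 0.167 | 0.333 |

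**4. Which reported figures move.** SAP 9.2 tabulates event counts, the quartiles and the 2-, 4-, 6- and 12-month rates. All landmarks lie before FU12. The 75% quantile is the time at which the curve reaches 0.25, so it can move only if S exceeds 0.25. In B with k = 1 it would be reported as reached at 5.0 years, although equal follow-up leaves the curve at 0.300 and the quantile unreached. In A, S is already below 0.25, so only the plotted tail and the event count change. The median could move only if S exceeded 0.5.

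**5. The July 2015 cut.** Protocol 4.2.2 cites earlier-trial data as of 11 May 2012. If no patient was dosed before that date, follow-up at the end of July 2015 is at most 3.2 years, short of even the 4.13-year lower limit for FU12.

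**The case against.** *The event date is an assumption.* SAP 9.2 says only that these patients count as events. A reader might infer that the plan as written sends the curve to zero, but it does not say so, and back-dating to the last assessment avoids it. This stands, and the conclusion is conditional on it. Dating at withdrawal remains the natural reading, since no response entry exists after FU12. The silence itself needs correcting.

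*Protocol 10.4 can be read two ways.* Taken literally, a withdrawal reason after FU12 would not be collected either, and the late event could not arise. That would conflict with Protocol 9.11.1 and SAP 8.1. If EOS data are collected, Protocol 10.5 includes a response assessment by physical examination, also for patients who stop treatment in remission. Should that count as a tumour assessment, some investigator-based censoring moves later than FU12. This stands for the investigator analysis. It gives no scan to the central read, and SAP 9.2 requires every secondary efficacy analysis on both.

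*The main analyses.* A reader might infer that the main PFS, TTP and DoR are biased because progression after FU12 goes uncounted. The documents do not support this. Stopping observation at FU12 for progressors and non-progressors alike is ordinary administrative censoring, and it is the remedy proposed here.

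*Small reach.* This is a sensitivity analysis of a secondary endpoint, in a descriptive study whose primary endpoint is ORR. Example A shows that no tabulated quantile or landmark need move. This is fair and limits the weight of the point.

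*Versions.* The SAP (3 April 2019) was written against Amendment 4, while the protocol supplied is Amendment 5 (26 May 2020). The documents do not show whether the data rule for the period after FU12 was already in Amendment 4. This may explain the gap but does not close it.

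**Conclusion.** The point holds in a limited form. In analyses done after patients pass FU12, the sensitivity PFS pairs a censoring rule that stops at the last tumour assessment with an event rule that has no time limit, so observation past FU12 depends on outcome. Dated at withdrawal, a single late progression can bring the curve to zero: 21.6% to 0% in one assumed example (18.0% with equal follow-up), and 33.3% to 0% in the other (30.0%). The direction follows from the rules; the sizes come from invented data.

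What can be affected is the tail, the event count and, if more than 25% are progression-free at FU12, the 75% quantile of the sensitivity PFS. The conclusion assumes that the withdrawal reason is still recorded after FU12 and that the event carries the withdrawal date. It is most secure for the central read. It does not extend to the main PFS, TTP or DoR, to the 2- to 12-month landmarks, or (if no patient had reached FU12 by then) to the July 2015 cut. It is worth settling before the analysis that follows the last EOS visit.

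**What to change.** Add to SAP 9.2 that a withdrawal for progression without radiological confirmation is dated at withdrawal, and that the sensitivity PFS, in both the investigator and the central-read version, is cut administratively at FU12 for all patients, with later events not counted. This takes a sentence or two and no new data. The cost is that a few late events go unused.

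Alternatively, amend Protocol 10.4 so that the date last known progression-free and the date of progression are entered in the eCRF for every patient treated beyond FU12, and use those dates for both censoring and events. This costs two date fields per continuing patient and no additional scans, and it keeps the late information. Those dates would come from the investigator, so for the central read the cut at FU12 is the cleaner choice.
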